### **3.4 Vulnerable subjects**

This study will only recruit subjects  $>65$  years. Subjects with lack of decision making capacity (as determined by the patient's oncologist) may be enrolled provided that they have a healthcare proxy who co-signs consent, attends study visits, and is available for follow-up phone calls.

---

## 4. SUBJECT IDENTIFICATION, RECRUITMENT, AND CONSENT

---

### **4.1 Identification and Recruitment**

We will recruit subjects using our group's established procedures. Before recruitment we will obtain approval by the Institutional Review Board (IRB). We will identify and recruit patients using medical records, advertisements in cancer clinics, and direct referral from nurses and physicians.

***Identification and recruitment via eRecord medical records and MyChart.*** We will identify potential patients who have completed cancer treatment for cancer  $\leq 10$  years prior to screening (i.e.  $\leq 10$  years of completing curative intent treatment).

Study personnel will screen medical records of potentially eligible subjects and confirm with/obtain physician permission to approach the patients. Alternatively, we will let potentially eligible subjects know about the study using MyChart for recruitment at the University of Rochester Medical Center.

Using the study inclusion/exclusion criteria, potential subjects will be identified using information available in eRecord. The study team will review eRecord data on these subjects in order to determine eligibility for this study. Data elements that will be reviewed include: patient's age, cancer diagnosis, last date of cancer treatment, and patient's race.

Potentially eligible subjects will receive an email or text notifying them that they have a new research opportunity available in MyChart. It can only be viewed after they log in to MyChart and visit the Research Studies page. Subjects will see a description of the study, which is included on the attached MyChart for Recruitment Request form (uploaded as part of recruitment materials). Underneath the study description on the Research Studies page, subjects will indicate whether or not they are interested in participating by clicking on the corresponding button. This will trigger a notification that is sent to the study coordinator's InBasket in eRecord.

Interested subjects will then be contacted for screening as described in this protocol. Subjects who are not interested will not be contacted and will be removed from the pool of eligible subjects. If subjects do not indicate whether or not they are interested in participating, they may be re-sent the email notification one additional time, no sooner than one week after the first email was sent.

When study accrual has been completed, outstanding research opportunities in MyChart will be rescinded.

#### **4.2 Screening**

A study staff member will meet the patient in person or via phone to explain the project, recruit, and screen per inclusion and exclusion criteria in *section 3.3*. We will obtain as much information ahead of time as possible from medical records. If we are meeting with the patient via phone, we

will familiarize the patient with our study and obtain basic eligibility information that was not obtained via medical records.

To ensure we do not approach the same subject twice, we will keep a screening log containing the following information:

- Screening ID (S1, S2, S3, ...)
- Subject name
- Date of contact
- Medical record number
- Gender
- Race/ethnicity
- Where/how we talked to the patient (e.g., phone)
- Whether the patient was eligible or not
- If ineligible, the reason they are ineligible
- Whether the patient consented or declined
- If declined consent, the reason for declining consent
- If consented, the subject ID in the study (C1, C2, C3, ...)

All subjects will need medical clearance from their oncologist (or designee) to participate in the intervention. To familiarize the clinical team with our study procedures we will provide a summary of the study protocol.

### **4.3 Consent process**

Current state, federal, and institutional regulations concerning informed consent will be followed. Three scenarios for consenting will be used.

#### ***4.3.1 Written Consent:***

For eligible patients who are interested in participating, a study member (coordinator, chair, co-investigator, etc.) will give the patient a copy of the IRB approved consent form. The consent form will be carefully reviewed including the duration of the study with the patient and health care proxy (if applicable) to ensure comprehension. If a patient lacks capacity, a health care proxy will be required to sign consent per institutional or local policies on consent for incapacitated/decisionally impaired subjects. If the patient does not have an appointed health care proxy on or before the

baseline visit, he/she will not be enrolled onto the study. All consent documents will be signed by the patient and/or designated health care proxy and maintained in the patient record with copies provided to the patient and/or designated health care proxy. The study member will be available to answer any questions the patient may have about any aspect of the study prior to consenting and throughout the entire study period. To reduce behavioral artifacts, we will blind subjects to our study's hypotheses using neutral language regarding the efficacy of the study drug on frailty and other outcomes. Patients may choose to sign the informed consent immediately on the day the study information is presented to them or they may choose to take the consent form home and discuss it with others. If a patient agrees to participate, a study team member or investigator and the subject will also sign the consent form. If the patient decides to take the consent form home they will receive a follow-up call from study personnel. If patient agrees to participate in the study, they may sign the consent form at the next meeting with the study team member or investigator. A copy of the signed consent form will be given to the subject. All consent documents will be maintained in the patient record.

#### ***4.3.2 Verbal Consent***

If the patient is not able to be approached at one of their survivorship oncology appointments, study personnel will call the patient using the IRB-approved telephone script for consent. The conversation and a copy of telephone script will be part of the subject's record. The patient will be given and asked to sign the full consent form at their next visit. This mechanism will minimize patient burden as they will not need to travel for an extra appointment to sign consent. It will also help to schedule study procedures in a timely way. The patient will also be given the option to complete the consent form by mail. See section 4.3.3

#### ***4.3.3 Mail Consent***

After completing the verbal consent, if the patient prefers to complete the consent form by mail then two consent forms will be mailed to the patient. The patient will also be sent a form with detailed instructions on completing the consent form and mailing back completed documents. Subjects are to sign both copies, and send both back with the provided mailing materials. Thus, the packet sent to the subject will contain:

- Two consent forms
- An informational letter with detailed instructions to correctly complete the consent form

- A self-addressed stamped envelope for the subject to include both signed copies of the consent forms

The consenting person will then sign both copies and either:

- Send one completed document (with both signatures) back to the subject by mail OR
- Give the subject at their next study visit

The second completed consent form will be added to subject's research folder. If after the verbal consent, the patient completes the written consent by mail it should be noted that there will be a difference in the dates of the signature for the patient and the coordinator.

After consent, additional study forms will be used to fully assess eligibility (e.g. forms associated with FFS).

#### **4.4 Registration**

For subjects who are eligible and who provide written informed consent or verbal consent, the following information will be entered into a master list using either Research Electronic Data Capture (REDCap) or another secure electronic database (e.g., password-protected Excel database on a password-protected networked drive). This information is needed to contact subjects during the study to troubleshoot any issues, remind them of study appointments, etc.:

- Subject ID number (used to identify the subject on all study forms and lab specimens)
- Subject name
- Subject phone number
- Subject email address
- Subject address of residence including nine-digit zip code
- Birth date (MM/DD/YYYY)
- Gender
- Race
- Cancer primary site
- Documentation of cancer stage, surgery, and completed cancer treatment regimen
- Most recent IRB approval date
- Name of person registering study subject
- Eligibility verification (FFS)

- Treatment facility
- All the information listed above in the Screening Log (*Section 4.2*)

---

## **5. METHODS AND STUDY PROCEDURES**

---

### **5.1 Overview of study**

This is a two arm RCT evaluating a 12-week nutritional supplement (EGCG) compared to usual care on inflammation, frailty, symptom burden, physical performance, and quality of life in 40 older patients who have completed curative intent cancer treatment. Subjects will complete questionnaires, clinical assessments, and a blood draw at two time points: baseline (week 0, T1) and post-intervention (approximately week 13, T2). After the subject is consented, they would complete the screening, where the subject will complete Fried's frailty measures to determine FFS and confirm eligibility. Subjects eligibility by the FFS must be confirmed before randomization, which will occur at the screening/baseline assessment. At the post-intervention assessment, subjects will be interviewed (with an optional audio recording) and will also complete a study feedback form.

To ensure appropriate safety precautions when conducting in-person study procedures, the process for conducting in-person visits outlined in the Guidance for Human Subject Research will be followed.

Some assessments will be conducted in the laboratory due to requirements of the facilities and equipment; some assessments will be conducted in Wilmot Cancer Institute clinics. Blood will be drawn by trained phlebotomists at UR-affiliated blood labs. The processing of blood samples will occur in the Cancer Control and Psychoneuroimmunology Lab (director: [name]), the Wilmot Cancer Center, or a UR-affiliated blood lab. Paper versions of the questionnaires can also be mailed to the patient's home prior to the baseline (week 0, T1) and/or post-intervention assessment (approximately week 13, T2) or completed in the Wilmot Cancer Institute clinics.

Due to safety precautions needed as a result of COVID-19, in lieu of some in person assessment, the virtual format of some assessments (such as SPPB and MoCA) will be conducted.

## **5.2 Timing of assessments**

Screening assessment T0 must be completed no more than 10 years after the completion of subject's curative intent cancer treatment. This timing is to ensure that lasting effects of curative intent cancer treatment immune system are minimized and that frailty is still likely to be present. This time frame is also consistent with other survivorship clinical trials.

Assessments T0 and T1 can be completed on the same day. In the event that assessment T0 and T1 are completed on different days, assessment T1 should not occur more than 4 weeks after T0. If for some reason T1 occurs more than 4 weeks after T0, Fried's frailty measures must be repeated to ensure that subjects still meet eligibility criteria. Optimally, assessments T0 and T1 will occur on the same day or within 1 week.

Optimally, assessment T2 will occur during week 13 (within the first week after the completion of study drug), but this may be adjusted (for to no more than 3 weeks after the completion of the study drug) to accommodate factors such as the clinical, subject, and researcher's schedule.

The following table details the approximate study timeline.

Table 1: Approximate study timeline															
Study week		0	1	2	3	4	5	6	7	8	9	10	11	12	13
Study activities	Consent T0	T1*													T2

\*Optimally T1 occurs within 1 week after T0 or on the same day.

## **5.3 Data collection tables**

The following table summarizes study activities based on the 12-week intervention that all subjects will complete regardless of randomization assignment (EGCG or usual care).

Assessment	Study Goal	Completed by	Screening	Baseline (week 0)	Post-Intervention (week 13)
			T0	T1	T2
Written Informed Consent	N/A	Subject	•		
Demographics	Eligibility	Subject	•		
Eligibility Checklist	Eligibility	Research Assistant	•		
Clinical Record Form	Eligibility A2/EA1	Research Assistant	•		

Fried's Frailty Score (FFS)	Eligibility/ A2/EA1	Research Assistant	●		●
GODIN Leisure-Time Exercise Questionnaire	Eligibility	Research Assistant	●		●
Instrumental Activities of Daily Living	GA/A2/EA1	Subject		●	●
Activities of Daily Living	GA/A2/EA1	Subject		●	●
Patient Rated Karnofsky Performance Status (Patient KPS)	GA/A2/EA1	Subject		●	●
Fall History	GA/A2/EA1	Subject		●	●
OARS Comorbidity	GA/A2/EA1	Subject		●	●
Social Activities	GA/A2/EA1	Subject		●	●
OARS Medical Social Support	GA/A2/EA1	Subject		●	●
Geriatric Depression Scale (GDS)	GA/A2/EA1	Subject		●	●
Generalized Anxiety Disorder-7 (GAD7)	GA/A2/EA1	Subject		●	●
Functional Assessment of Cancer Therapy: General (FACT-G)	EA2	Subject (diagnosed with any cancer except colorectal)		●	●
Functional Assessment of Cancer Therapy: Colorectal Cancer (FACT-C)	EA2	Subject (diagnosed with colorectal cancer)		●	●
MD Anderson Symptom Inventory (MDASI)	EA2	Subject		●	●
Mini Nutritional Assessment (MNA)	GA/A2/EA1	Research Assistant		●	●
Physician Rated Karnofsky Performance Status (KPS)	GA/A2/EA1	Research Assistant		●	●
Labs	GA/A2/A3/EA1/EA3	Chart Review		●	●
Blood Requisition Form	A3 & EA3	Phlebotomist		●	●
Montreal Cognitive Assessment (MoCA)	GA/A2/EA1	Research Assistant		●	●

Short Physical Performance Battery (SPPB)	EA2	Research Assistant		•	•
Timed up and Go	EA2	Research Assistant		•	•
Yale Physical Activity Survey for Older Adults	EA2	Research Assistant		•	•
Qualitative Interview (Audio Recorded)	EA4	Research Assistant			•
Pill Count Form (Excel)	A1	Research Assistant			•
Weekly Phone Call Log (Excel)	A1	Research Assistant		•	•
Study Feedback Form	A1	Subject			•
Not Applicable (N/A); Geriatric Assessment (GA); Aim 1 (A1); Aim 2 (A2); Aim 3 (A3); Exploratory Aim 1 (EA1); Exploratory Aim 2 (EA2); Exploratory Aim 3 (EA3); Exploratory Aim 1 (EA4)					

#### **5.4 Screening assessment (T0)**

Fried's frailty measure will be completed after consent is obtained from the subject in order to confirm eligibility. Fried will be characterized as a combination of symptoms (such as low energy, weakness, slower walking speed, reduced participation in activities, and weight loss). This measure should take 5-10 minutes to complete. The following will be used to determine the subjects Fried's Frailty Score (FFS) and will be reassessed during the post-intervention (T2) assessment.

**Table 3: Fried Frailty Score (FFS)**

Slowness	time to walk 4 meters based on height: $\leq 0.65\text{m/s}$ for height $\leq 1.59\text{m}$ ; $\leq 0.76\text{ m/s}$ for height $>1.59\text{m}$
Weakness	grip strength/body mass index (BMI): $\leq 17$ for BMI 23-26; $\leq 18\text{kg}$ for BMI 26-29; $\leq 21\text{kg}$ for BMI $>29$
Weight loss	$>10\text{lb}$ lost unintentionally in the last year/last visit or BMI $<18.5$
Physical Activity	GODIN Leisure Score Index- Activity/week: Score $\leq 23$ equivalent to $<14\text{ Kcal/kg/week}$
Fatigue	answer yes to any of the following (low usual energy level; unusually weak or tired in the last month)

FFS will be assessed using the 5 characteristics listed in Table 3. For each characteristic, subjects will receive a score of one if they met the cut-off for that characteristic. The scores will be summed. Total scores can range from zero to five to represent FFS, with zero indicating that they did not

meet any cut offs, and five meaning that they met all five cut offs. FFS was chosen because it can quickly assess frailty in outpatient settings, has good construct, convergent, concurrent, and predictive validity, and is sensitive to change following an intervention. Subjects can be classified into three frailty groups based on the FFS: FFS= 0 is classified as robust/not frail, FFS= 1 or 2 classified as pre-frail, and FFS= 3-5 classified as frail.

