### **3.3 Inclusion and exclusion criteria**

#### **Inclusion Criteria: Study subjects must:**

1. Be age 65 or over.
2. Be diagnosed with stage I-III Cancer
3. Have completed curative intent treatment  $\leq 10$  years prior to screening
  - Patients on endocrine therapies are allowed to enroll
4. Have a Fried's Frailty Score (FFS) of  $\geq 2$
5. Able to provide informed consent, or have consent given by patient-designated health care proxy per institutional policies and University of Rochester Cancer Control URCC guidelines.

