### 11.1 Sample size determination

We plan to enroll 40 subjects (20;  $\geq 6$  AA/B per arm). Evaluation of recruitment and adherence to the intervention is required for planned future Phase 2/3 frailty trials in older cancer survivors.

*Aim 1:* With a feasibility target of 70% of

Protocol Date: January 2016

44

randomized subjects completing the study we expect at least 14 evaluable patients per arm, which is appropriate for small randomized studies and it will allow us to obtain preliminary estimates of descriptive statistics (mean, standard deviation (SD), and confidence intervals (CI)). *Aim 2:* At significance level  $\alpha=0.15$ ,  $N=14$  per arm will provide 70% power to detect effect size (standardized mean change in frailty score) of 0.66, if pre-post correlation=0.5 (conservative estimate for FFS; Figure 5).

**Analyses:** *Aim 1:* For each feasibility outcome (recruitment and adherence), we will evaluate proportions of subjects meeting criterion and report percentages with CIs. For AEs, we will report the total and severity of AE's per group. *Aim 2:* Descriptive statistics will be calculated at baseline, post-intervention, and for pre-post change scores for subjects in EGCG and UC arms. To evaluate the preliminary efficacy estimates of EGCG on FFS we will use an analysis of covariance (ANCOVA) model (outcome=FFS at post, covariates: FFS at baseline and arm). Estimates of distribution characteristics (e.g., mean, variance, pre-post correlation) and preliminary estimates of efficacy will inform the design and sample size of our planned future study. *Aim 3:* Similar analyses to Aim 2 will be performed for TNF- $\alpha$ , TNFRI, TNFRII, IL-6, IL-1 $\beta$ , and CRP. If data for inflammatory markers are missing due to lower limit of detection, we will use appropriate imputation methods. *Aim 4:* Using similar analyses to Aim 2, we will conduct preliminary subgroup analyses by race and treatment type.

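### Table 3 gives no grip cut-off below BMI 23, so read literally the weakness item cannot be scored there; FFS entry and outcome are affected, probably modestly

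*Combined protocol and SAP*

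**What the plan says.** Protocol section 5.4, Table 3, gives the weakness row as "grip strength/body mass index (BMI): $\leq 17$ for BMI 23-26; $\leq 18\text{kg}$ for BMI 26-29; $\leq 21\text{kg}$ for BMI $>29". The lowest band starts at BMI 23, and no other section supplies a grip cut-off.

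The scoring rule below the table is that "subjects will receive a score of one if they met the cut-off for that characteristic", and "Total scores can range from zero to five to represent FFS". The weight-loss row of the same table scores a subject with weight "lost unintentionally in the last year/last visit or BMI $<18.5", so the table expects thin subjects. The only grouping given is "FFS= 1 or 2 classified as pre-frail, and FFS= 3-5 classified as frail".

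FFS has two main uses:

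- **Entry.** Inclusion criterion 4 in section 3.3 reads "Have a Fried's Frailty Score (FFS) of" at least 2, and section 5.1 adds that "Subjects eligibility by the FFS must be confirmed before randomization". Neither the inclusion nor the exclusion list mentions BMI.
- **Outcome.** The Aim 2 analysis of covariance in section 11.1 is specified as "outcome=FFS at post, covariates: FFS at baseline and arm". It is the only comparison with a stated power.

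Section 2.3, Exploratory Aim 3, also compares pre-frail with frail survivors. Section 5.5 has weight measured at T0 and again at T2.

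**The concern.** A subject below BMI 23 has no grip threshold to meet. Under the literal rule the item then scores 0 however weak the grip. That conflicts with the stated 0 to 5 range, makes entry harder for thin subjects than for others with the same deficits, and moves some of them from frail to pre-frail.

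The outcome is affected too. BMI is recalculated when weight is retaken at T2. A weak subject whose BMI falls below 23 loses a point, and one whose BMI rises past 23 gains a point, with no change in grip.

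Two smaller faults sit in the same row. A BMI of exactly 26 has two cut-offs, 17 and 18, and the first cut-off lacks the kg shown on the other two.

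**Working it through.** **The plan's own figure.** Inputs from sections 11.1 and 11.2: 14 evaluable per arm, standardised effect 0.66, pre-post correlation 0.5, two-sided alpha 0.15, analysis of covariance.

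- Residual SD = sqrt(1 − 0.5²) = 0.866, so the effective effect is 0.66/0.866 = 0.762.
- Noncentrality = 0.762 × sqrt(14/2) = 2.016, with 2 × 14 − 3 = 25 df.
- Power = 70.4%. The stated 70% reproduces.

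**What follows from the rule alone** (BMI below 23, weakness scored 0):

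- Maximum FFS is 4.
- Of the C(5,2) = 10 ways to have exactly two deficits, C(4,1) = 4 include weakness. These score 1 and fail entry.
- Of the C(5,3) = 10 ways to have exactly three, C(4,2) = 6 include weakness. These drop from frail to pre-frail.

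These are counts of patterns, not probabilities.

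**Exclusion among truly eligible subjects below BMI 23.** The documents give no prevalences, so these are assumed. The excluded fraction is P(weak and exactly one other deficit) / P(at least 2 of 5).

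For independent items of equal prevalence q, the numerator is q × 4q(1 − q)³. At q = 0.3 this is 0.1235/0.4718 = 26.2%. At q = 0.5 it is 0.125/0.8125 = 15.4%. With correlated items (a shared normal factor; items independent given the factor):

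| Correlation | q = 0.3 | q = 0.4 | q = 0.5 |
|---|---|---|---|
| 0 | 26.2% | 20.8% | 15.4% |
| 0.3 | 19.0% | 15.5% | 12.1% |
| 0.5 | 15.2% | 12.5% | 10.0% |

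If weakness is rarer (0.1 to 0.2) and the other items stay at 0.3 to 0.5, the range is 0.7 to 19.1%.

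**Share of all eligible subjects**, assuming 10 to 30% are below BMI 23:

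- Equal prevalence: 0.10 × 10.0% = 1.0% to 0.30 × 26.2% = 7.9%.
- Rarer weakness: 0.10 × 0.7% = 0.07% to 0.30 × 19.1% = 5.7%.

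**Frail labelled pre-frail**, below BMI 23: P(weak and exactly two others) / P(at least 3 of 5) is 20.0 to 48.7% with equal prevalence, and about 3 to 39% with rarer weakness.

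**Power when the item scores 0.** Two approximations:

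- Spread the effect equally over the five items, with a fraction f of subjects unable to change on weakness. The effect becomes 0.66 × (1 − f/5). For f = 10%, 20%, 30% it is 0.647, 0.634, 0.620, with power 69.0%, 67.6%, 66.2%. The loss is 1.4 to 4.2 points.
- Simulate five binary items (q = 0.3 or 0.5, correlation 0 to 0.5, 20,000 trials). The loss is 0.3 to 0.8 points at 10% affected and 1.0 to 2.5 points at 30%. Power with all items intact varied from 69.9 to 81.2% across scenarios, so this gives only an order of magnitude.

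**Power when the item is undefined and the subject is dropped** (section 11.2 reports complete cases): 67.7%, 64.9%, 61.8%, 58.5% with 13, 12, 11, 10 per arm.

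**The case against.** The strongest objection is that the table may have lost a band when the PDF was converted to text. The missing unit sits on the first listed cut-off, next to where a lower band would stand. The row otherwise reads as one continuous list. This cannot be settled from the converted text, so checking the source table comes first.

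A second objection is that this is a small feasibility trial tested at alpha 0.15, that Aim 2 seeks preliminary data, and that the Deficit Accumulation Frailty Index is a second frailty measure. All of that is true and limits the consequence. It does not make the entry rule or the FFS outcome well defined. Likewise, any banded rule has steps at its edges, but at BMI 23 the cut-off does not step; it disappears.

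A reader might infer stronger conclusions that the documents do not support:

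- **Power falls to 58.5%.** This needs subjects with an undefined item to be randomised on the other four items and then dropped. Section 5.1 requires FFS eligibility before randomisation. If it cannot be confirmed they do not enter, others take their places, and no power is lost this way. The literal scoring rule also favours a score of 0 over an undefined item.
- **The treatment comparison is biased.** The gap is the same in both arms. Section 1.2 mentions weight loss with 12 weeks of EGCG, but in adults with obesity, not in subjects near BMI 23.
- **The cut-offs are wrong for men.** Half the planned sample is male, and the reference cited at the scoring step is by its title a study of older women. A title does not settle whether sex-specific cut-offs are needed.
- **BMI cannot be computed in time.** Section 5.5 places height at baseline, but baseline precedes randomisation and may fall on the screening day.

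**Conclusion.** The point stands in a limited form. As printed, the weakness row leaves BMI below 23 without a cut-off and gives BMI 26 two. Applied literally, it contradicts the stated 0 to 5 range and mis-scores both entry and the Aim 2 outcome for thin subjects. That conclusion needs no assumption beyond the table being complete.

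The size does rest on assumptions: item prevalences, their correlation, and a 10 to 30% share below BMI 23, none of which the documents give. On those, roughly 0.1 to 8% of eligible subjects are excluded, at most about 3 in every 40 (7.9% × 40 = 3.2). Power falls by about 0.3 to 4 points, depending on the method. The stated power is correct, and no bias between arms is shown. It should be fixed because the score decides entry and the repair is cheap.

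**What to change.** 1. Check the source table for a BMI band lost in conversion.
2. If there is none, reconcile the weakness row with its named source, so that the BMI bands cover all values without gap or overlap and every cut-off carries its unit. No cut-off is proposed here.
3. If subjects are already enrolled, re-score FFS at T0 and T2 from recorded grip, height and weight, keep subjects as randomised, and report both scorings.

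The cost is a change to one table row and a short re-score. The downside is that a few subjects may change score or eligibility status.
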